2.1.3.5 Secondary MicrobiomeAnalysis

Secondary Analysis for all types and timepoints of microbiome samples will include:

- L1-norm distance PERMANOVA on bacterial reads
- For RNA-sequenced data: L1, L2-norm distances on virus, parasites, fungi.
- Simpson's and Shannon's estimated gamma diversities (transformed into effective number) will be compared by arm using a permutation test without correcting for baseline (ie post test only)
- Conjunctiva swabs, 16S-sequencing at 24-months will be conducted on individual samples. We will use PERMANOVA on an L1-norm distance on bacterial OTUs to determine if treatment significantly explains the difference between the two groups.
- TAC-card for rectal specimens of bacteria and viruses between two treatment groups at 24 months and at basline (PERMANOVA), and similarly for NP swabs (i.e., TAC-card)

Secondary analysis for rectal swabs at 36-months

We propose to compare the normalized abundance of MLS reads between treatment arms. Resistance to other classes of antibiotics will be compared. In addition, we will also assess for a difference in the normalized abundance of betalactams reads. P-values will NOT be corrected for multiple comparisons. Instead, we will estimate the FDR for resistance to each class of antibiotic.

2.1.3.6 Clinic-Based Case Findings

Clinic-based case finding will use consecutive cases from all CSIs in Loga district. Consecutive cases of infectious illnesses among 0-5 year-old children will be assessed from the case log from months 0 to 12. The number of cases of infectious illness per randomization unit will be compared for 1 calendar year between the intervention and control groups in a Poisson regression, adjusting for the number of cases of infectious illness recorded in the calendar year preceding the start of the intervention.

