2.1 Planned Analyses

2.1.1 Mortality Trial

The primary prespecified analysis will use the number of deaths in each community as the outcome variable. For analysis, a death is counted when an individual in the target age range 1–59 months (inclusive) is on census and is not on the next census due to death. Census 0 takes place at the beginning of the study, and each subsequent census takes place approximately six months later. The outcome variable is derived by summing the deaths in each period.

Primary Analysis (Mortality Study).

The primary analysis will be conducted as negative binomial regression. The number of personyears (for persons in the target age range) is derived by summing the person-times for each period. The community-level predictor consists of treatment arm for the community. Specifically, the treatment variable is a community level variable, not an individual level variable. An additional categorical regressor will be included for the country. The likelihood-ratio will be computed, and the statistical significance assessed by permutation testing. Specifically, we will assess the significance of including treatment arm at a two-sided level of 0.05 (a mortality effect in either direction will be statistically significant). The number of permutations is chosen as 10,000, large enough to minimize Monte Carlo error; consecutive runs using a prespecified seed will be reported (and if the Monte Carlo confidence interval for the P-value includes the value 0.05, a new set of 100,000 runs will be conducted and the value reported). An estimated aggregation parameter over 30 will result in the choice of Poisson regression. Evidence of poor fit (based on deviance and/or score residuals) will result in reporting of additional models, beginning with estimation of country-specific aggregation parameters. (Note that the primary analysis remains the single multi-country negative binomial regression, with permutation-based significance testing.)

Individuals who are in the target age range at the beginning of any study period, but who are no longer in the target age range by the end, are considered to be fully enrolled and contribute the full amount of person-time for that period.

All three sites will be aggregated together for the single primary prespecified analysis. The intent is a single negative binomial regression for all three countries together, as the single outcome of the trial.

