Model adequacy will always be checked (e.g. overdispersion for count models), and leaveone-out influence plots will be conducted to indentify highly influential single observations. All analyses in this trial will always account for the clustered (community randomized) design.

In the event of an unanticipated rare event (such as a natural disaster or bus accident) in part of an area, sensitivity analysis will be conducted. Analysis omitting this region will be reported, as well as a stratified permutation test in which we compare treatment and control within strata defined by the affected region. While entirely unsuitable for primary analysis, under certain circumstances it may be possible to remove mortality due to the rare event; we would propose reporting this analysis as well.

Secondary Analyses (Mortality study)

All secondary analyses will be sharply distinguished from the primary prespecified analysis and are as the following:

1. Age, treatment group, and country will be used as a covariates in the primary analysis model.

- 2. Negative binomial regression for each time period will be analyzed, using time, country, and treatment.
- 3. A Poisson regression at the individual level comparing treatment groups, using each period of time.
- 4. Negative binomial regression contrasting the first and second years.
- 5. Negative binomial regression using a country-treatment interaction.
- 6. Treatment effect by age will be analyzed using subroups of patients defined by the following age brackets: [1, 6), [6-12), [12-18), [18-24), [24, 60). Age of the child will be the age captured at enrollment.
- 7. We will compare the cause of death, as determined by Verbal Autopsy, between the two arms, using a 2 x k table, permuting by randomization unit.
- 8. Analyses will be conducted for each country, using data from that country only. This analysis will be negative binomial regression with treatment assignment for each village as the covariate.
- 9. An on-treatment analysis of mortality will be restricted to those taking the medication (or placebo) (i.e., comparing placebo-takers to medication-takers).
- 10. Analysis of those censused but too young to treat will be conducted.
- 11. Data will be formatted to include the Phase 24 vital status of all persons found alive at any of the Phases 0, 6, and 12 (with no indication of them dying in the interim) instead of *only considering the vital status of persons alive at phase 18* census.

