The analysis will follow these guiding principles: (1) All data from all available participants will be included, regardless of whether the patient contributed data to all time periods, or to only a subset of periods; (2) The analysis must reflect the longitudinal nature of the followup and the clustered nature of the design, (3) Permutation testing will be used to compute the P-value, (4) The model must be fully prespecified prior to any analysis of any kind.

If a village randomized to the morbidity study has fewer than 40 children upon census, an additional morbidity village may be recruited in its place.

All secondary analyses are identified as the following:

- 1. Repeated measures of outcomes for children present at baseline and possibly followed for 24 months. using 0, 12, and 24-month measurements (or all time points processed).
- 2. Analyze additional outcomes: WHO z-values (height for age, weight for height, weight for age) and MUAC. P-value will be adjusted for these additional outcomes.
- 3. Separate outcome using cross-sectional post-test children 25 months and under using 0.05 alpha. Analysis will be similar to longitudinal (height for age, weight for height, outliers, etc. Note that these children were not eligible for the primary analysis.
- 4. Community-level varaiables will be considered from CSI records.
- 5. Per-protocol analysis will be performed by arm, i.e. only including those who took the treatment.
- 6. Other outcomes by treatment arm at 24 months will include percent wasted and percent stunted. Permutation p-values will be computed here.

Sensitivity analysis including the outliers as well as dissociating the measurements in a repeated measures analysis will be conducted. Appropriate consideration will be analyzed for transfromation, heteroskedacity, and outliers. Additional prespecified secondary analyses are listed on www.clinicaltrials.gov.

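### The clinic case-count analysis names a Poisson regression but does not say how extra variation between communities enters the P-value and the interval

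*SAP*

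**What the plan says.** SAP 2.1.3.6 describes the data source: "Clinic-based case finding will use consecutive cases from all CSIs in Loga district". The outcome is "The number of cases of infectious illness per randomization unit", and these counts "will be compared for 1 calendar year between the intervention and control groups in a Poisson regression". The only covariate named is each community's case count from the year before treatment began. The section gives no variance method, P-value method, population offset or alpha.

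Three statements elsewhere in the SAP bear on it:

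- **Section 2.1.1, general clauses.** "All analyses in this trial will always account for the clustered (community randomized) design". Also "Model adequacy will always be checked (e.g. overdispersion for count models"; no consequence of that check is stated for the clinic counts.
- **Section 2.1.1, primary mortality analysis.** Deaths per community are analysed by negative binomial regression with permutation testing. Poisson is used only if the estimated aggregation parameter exceeds 30.
- **Section 2.1.2, morbidity.** One of the guiding principles is "Permutation testing will be used to compute the P-value". The section also treats a village-level analysis as already accounting for clustering.

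**The concern.** With one count per community, a Poisson regression sets the residual variance equal to the mean. Community-to-community differences that the prior-year count does not explain then have no place in the standard error. Analysing by community gives the right unit, but not the right variance. The SAP recognises this for deaths, where Poisson is the exception. For clinic cases Poisson is the only model named, and no reason is given for the difference. What is at stake is the P-value and interval for the effect on recorded childhood illness in Loga: too small a standard error makes a chance difference look like an effect, or makes an effect look more precise than it is.

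**Working it through.** **No figure to reproduce.** The SAP gives no sample size, power or error rate for this analysis. Its general cluster formula (SAP 3.1) does show how it treats between-community variation: it adds k²(λ₀² + λ₁²) to the Poisson term (λ₀ + λ₁)/y. For Niger, λ₀ = 0.02, λ₁ = 0.017, k = 0.51 and y = 668 × 0.167 × 2 years × 0.95 = 212.0:

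c = 1 + 7.849 × (0.037/212.0 + 0.2601 × 0.000689)/0.003² = 309.5, so 310 per arm.

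With 0.90 in place of 0.95, y = 200.8 and c = 318. The SAP states 312. So k is variation on top of Poisson noise, which is how it is used below.

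**Inputs**

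- Between-community CV: 0.51 (SAP 3.1.2, planning) and 0.34 (Contingency Study SAP, Study A, observed in Niger). Both are for mortality and serve as proxies for clinic cases.
- Two-sided alpha of 0.05, borrowed from the mortality analysis ("we will assess the significance of including treatment arm at a two-sided level of 0.05").
- Assumed, because the documents give none: mean cases per community μ of 5, 20 or 50; 15 or 100 communities per arm; year-to-year correlation ρ of 0.5 or 0.8.

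**Formula without adjustment.** The variance of a count is μφ with φ = 1 + μ·CV². A Poisson Wald test with model-based errors then has type I error 2 × [1 − Φ(1.96/√φ)]. For μ = 20 and CV = 0.34: φ = 1 + 20 × 0.1156 = 3.31, 1.96/1.82 = 1.077, and the error is 28%.

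**Simulation with adjustment.** Null trials (2,000 per setting) used log-normal community effects and the log prior-year count as covariate. Entries are type I error with model-based Poisson errors; paired values are 15 / 100 communities per arm.

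| CV | μ | φ | Unadjusted (formula) | Adjusted, ρ = 0.5 | Adjusted, ρ = 0.8 |
|---|---|---|---|---|---|
| 0.34 | 5 | 1.58 | 11.9% | 11.2 / 10.3% | 10.1 / 9.1% |
| 0.34 | 20 | 3.31 | 28.1% | 24.2 / 23.9% | 19.4 / 19.6% |
| 0.34 | 50 | 6.78 | 45.2% | 39.4 / 41.9% | 31.3 / 30.6% |
| 0.51 | 5 | 2.30 | 19.6% | 17.9 / 17.8% | 13.8 / 14.1% |
| 0.51 | 20 | 6.20 | 43.1% | 38.7 / 40.1% | 29.3 / 29.8% |
| 0.51 | 50 | 14.01 | 60.0% | 57.4 / 54.4% | 42.5 / 42.4% |

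Taken together with further runs over the same settings, including the prior-year count entered unlogged, the ranges are about 8-20% at μ = 5, 19-41% at 20 and 27-59% at 50. The number of communities hardly matters. At ρ = 0.95 the error is still about 9-28%.

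**Where the excess is small.** Without adjustment, μ = 2 gives 7.7% at CV 0.34 and 5.2% at CV 0.10.

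**At the SAP's own Poisson threshold.** An aggregation parameter of 30 means CV = 1/√30 = 0.18. Without adjustment, φ = 1 + 20/30 = 1.67 gives 13% at μ = 20, and φ = 1 + 50/30 = 2.67 gives 23% at μ = 50.

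**Remedies in the same null trials.** Scaled (quasi-Poisson) errors gave about 4-7% (3-10% in the further runs) and robust errors about 4-7%. Permuting arm by community gave about 5-7% (15 per arm, ρ = 0.8, 1,000 trials, Monte Carlo error about 0.7 points). Negative binomial regression itself was not simulated.

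**Interval.** A permutation P-value leaves the Poisson interval unchanged. Without adjustment that interval is 1/√φ of its proper width: 1/√3.31 = 0.55 at μ = 20 and CV 0.34. Adjustment narrows the gap but does not close it.

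**The case against.** A reader might infer that the plan ignores variation between communities, and that a null effect would therefore be declared significant far more often than 5% of the time. The documents do not support that.

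- The clustering clause in SAP 2.1.1 sits in the mortality section but is worded for the whole trial. An analyst who found overdispersion and still reported plain Poisson errors would hardly be honouring it.
- The permutation rule in SAP 2.1.2 plausibly reaches this analysis. Protocol 5.2.2 and 18.1 place clinic-based case finding in the morbidity study, and SAP 2.1.2 lists community-level variables from CSI records among its secondary analyses. The placement of 2.1.3.6 under Microbiome looks like an accident of numbering. Under permutation the level is about 5%.
- Protocol 5.2.2 makes this a non-core activity, and SAP 2.1.2 requires Steering Committee approval of non-core analysis plans. Section 2.1.3.6 may not be the full specification.
- The prior-year count absorbs part of the variation, including much of the difference in community size. A reader might see the missing offset as a flaw, since Protocol 4.1 admits communities of 200 to 2,000 people. Under randomization it is a matter of precision.

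All of this stands against the strong reading. It does not settle the narrower point. The clustering clause names no method, and SAP 2.1.2 shows that village-level analysis alone may be taken to satisfy it. The overdispersion check has no stated action here. Permutation repairs the test only. The morbidity principles, if they apply, also require the model to be fully specified before any analysis.

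**Conclusion.** The point holds as a gap in specification with a potentially large consequence. SAP 2.1.3.6 names a Poisson model and states no provision for extra-Poisson variation. Run with model-based errors, it would exceed the 5% level under most plausible inputs, by the amounts in the working.

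Those amounts rest on mortality CVs used as proxies and on assumed case counts, correlations and numbers of communities. Few cases per community or a small residual CV would make the excess slight, and a permutation P-value would largely remove it from the test while leaving the interval too narrow. The severity is lower because this is one non-core Niger outcome; neither the primary mortality result nor the primary morbidity outcomes listed in SAP 2.1.2 depend on it.

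**What to change.** Replace the model in SAP 2.1.3.6 with the SAP's own mortality template: negative binomial regression on community counts (or Poisson with scaled or robust errors), adjusted for the log prior-year count with a small constant such as 0.5 added for zeros. Take the P-value from permuting community labels, and report an interval that reflects overdispersion, so that test and interval rest on the same variance. State the alpha and that the analysis follows the morbidity principles. A log child-population offset is an optional gain in precision.

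The cost is a sentence or two in the SAP and no new data; the offset, if used, would draw on the census. Intervals will be wider where communities differ beyond Poisson noise, which is the honest width.

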2.1.3.7 Clinic-Based NP swabs

Clinic-based NP swabs. We will collect nasopharyngeal swabs from children residing in morbidity communities who present to the CSI with respiratory complaints within the month of the annual morbidity assessment (i.e., month 0, 12, 24), and process swabs for macrolide resistance. The primary analysis will compare macrolide resistance in the azithromycin versus placebo groups using mixed effects regression as described above. As a secondary analysis, we will compare the prevalence of macrolide resistance in clinic-based swabs vs. community-collected swabs in a mixed effects regression, with a permuted p-value that accounts for the stratified nature of the data.

2.3 General considerations

Individual level missing data (due to loss to follow-up or droputs) is expected. If an individual is lost to follow-up or otherwise unavailable during an interval of length D, then the individual is assumed to contribute the amount of person-time D/2 to the denominator (midpoint imputation).

Village-level missing data could occur for various reasons, including field error, withdrawal of support from village leadership, and so forth. While this has not happened in previous studies in our group, the analytic plan will be to analyze all available information (including data from any village prior to the time of dropout of that village). Sensitivity analysis will be conducted in which various values are imputed to the missing observations to determine how our conclusions would change.

3 Sample Size Planning

3.1 Mortality trial

We use the following formula (cited from Cluster Randomised Trials Hayes RJ, Moulton LH),:

$$c=1+\left(z_{\alpha/2}+z_{\beta}\right)^{2}\frac{(\lambda_{0}+\lambda_{1})/y+k^{2}(\lambda_{0}^{2}+\lambda_{1}^{2})}{(\lambda_{0}-\lambda_{1})^{2}}$$

where

c is the number of clusters per arm,

y is the number of person-years per cluster,

 λ_0 is the rate in the control group,

 λ_1 is the rate in the treatment group,

k is the coefficient of variation in both groups,

 α is the alpha level,

 β and is the type II error rate.

3.1.1 Malawi

- The base rate for mortality is assumed to be 0.0148 per year in the target age range.
- We assume the same coefficient of variation for village-level mortality as for the Niger site, i.e. 0.51.
- We assume that 19% of the population is in the target range of 1–59 months (inclusive) for the Malawi site.
- We assume an average community size of 799 people.
- We assume 10% loss to follow-up per year.
- The effect size is 0.15.
- The desired power is 80%.

The number of clusters per arm for Malawi is 310, the total number of clusters for Malawi is 620, and the expected total number of children involved is 94122. In practice, we allow that these are estimations and will depend on drug/placebo availability, with the request being for 83,333 doses per country, assuming 3 doses per 30ml bottle of suspension.

Supplementary assessment, June 2016: In practice the Malawi villages effective size is 1464 individuals, with a slightly higher baseline mortality rate of 0.005 per year. The sample size of 306 randomization units in both arms appears to give approximately 41% power for an effect size of 15% for Malawi alone.

3.1.2 Niger

The input assumptions are as follows:

- The base rate for mortality is assumed to be 0.02 per year in the target age range, lower than seen in the PRET study in Niger.
- We assume the coefficient of variation for village-level mortality is 0.51 (derived from PRET Niger data).
- We assume that 16.7% of the population is in the target range of 1–59 months (inclusive)for the Niger site. National statistics suggest a slightly higher fraction (19%), which would yield fewer communities than we are planning for.
- We assume an average community size of 668 people. The communities are known as *grappes*.
- We assume 10% loss to follow-up per year (source: PRET Niger, [name], pers. comm.).
- The effect size is 0.15.
- The desired power is 80%.

The number of clusters per arm for Niger was projected to be 312, the total number of clusters for Niger was projected to be 624, and the expected total number of children involved was projected to be 69472. In practice, we allow that these are estimations and will depend on drug/placebo availability, with the request being for 83,333 doses per country, assuming 3 doses per 30ml bottle of suspension. These may be underestimates because of the short interval and the lack of a rainy season.

The final randomization list contained 646 communities, 30 of which were randomized to the morbidity study.

Supplementary assessment, June 2016: In practice the Niger villages appear to have an average of 688 individuals, with a slightly higher baseline mortality rate of 0.025 per year. The sample size of 622 randomization units in both arms appears to give approximately 84% power for an effect size of 15% for Niger alone.

3.1.3 Tanzania

The input assumptions are as follows:

- Considerable uncertainty exists in the base rate for mortality, with national estimates substantially lower than estimates for nearby regions within the country. For planning, we chose a rate of 0.016 per year in the target age range, but recognize that if the true mortality rate is lower, we will have lower power.
- We assume a smaller coefficient of variation for village-level mortality than for the Niger site. Specifically, this value is 0.4, as determined by consultation with the Johns Hopkins team.
- We assume that 17% of the population is in the target range of 1–59 months (inclusive) for the Tanzania site.
- We assume an average community size of 600 people. The communities are known as *hamlets*.
- We assume 10% loss to follow-up per year.
- The effect size is 0.15.
- The desired power is 80%.

The number of clusters per arm for Tanzania was projected to be 307, the total number of clusters for Tanzania was projected to be 614, and the expected total number of children involved was projected to be 62628. In practice, we allow that these are estimations and will depend on drug/placebo availability, with the request being for 83,333 doses per country, assuming 3 doses per 30ml bottle of suspension.

The final randomization list contained 644 communities, of which 30 were randomized to the morbidity study.

Supplementary assessment, June 2016: In practice the Tanzania randomization units appear to have an effective size of individuals, with a slightly higher baseline mortality rate of 0.006 per year. The sample size of 631 randomization units in both arms appears to give approximately 31% power for an effect size of 15% for Tanzania alone.

Note that the primary analysis is all countries together. We anticipate more than 80% power to detect an effect size of approximately 0.10, or ten per-cent.

Update: 2016. We anticipate approximately 80% power to detect an overall effect of 14%, accounting for changes in recruitment and mortality.

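### The 2016 pooled power statement (80% at a 14% effect) does not fit the SAP's own country powers, which give about 93% at 14% and 80% at about 11.5% under the planned country-adjusted model.

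*SAP*

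**What the plan says.** SAP section 2.1.1 makes one negative binomial regression over all three countries the primary analysis, tested at two-sided 0.05. On adjustment it says: "An additional categorical regressor will be included for the country".

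Section 3.1 sizes each country separately for a 15% effect. Section 3.1.3 then gives the planning statement for the pooled analysis: "We anticipate more than 80% power to detect an effect size of approximately 0.10, or ten per-cent".

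In June 2016, with the trial running, each country was reassessed at 15%:

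- Niger, 622 units: "appears to give approximately 84% power for an effect size of 15% for Niger alone".
- Malawi, 306 units: "appears to give approximately 41% power for an effect size of 15% for Malawi alone".
- Tanzania, 631 units: "appears to give approximately 31% power for an effect size of 15% for Tanzania alone".

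The pooled statement was then replaced by: "Update: 2016. We anticipate approximately 80% power to detect an overall effect of 14%, accounting for changes in recruitment and mortality". No formula, inputs or pooling method accompany it.

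The reassessment describes the Malawi rate as "with a slightly higher baseline mortality rate of 0.005 per year" and the Tanzania rate as "with a slightly higher baseline mortality rate of 0.006 per year". The planning rates in the same sections are 0.0148 and 0.016.

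**The concern.** Niger at 84% for a 15% effect already has close to 80% power for a 14% effect by itself. A pooled analysis that adds 306 Malawi units and 631 Tanzania units should do clearly better, because the country term removes differences in rate between countries and leaves information on the common rate ratio to add up. A pooled figure of 80% at 14% leaves almost nothing for those two countries.

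The stakes are in interpretation. A reader sees the detectable effect move from below 10% to 14% and concludes that falling mortality cost the trial most of its reach. A null result would also be read as uninformative for effects between about 11.5% and 14%, which the trial is in fact powered to detect.

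**Working it through.** **1. The country figures reproduce.** The SAP formula in section 3.1, solved for power, is

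power = Phi( sqrt[ (c - 1)(λ0 - λ1)² / ((λ0 + λ1)/y + k²(λ0² + λ1²)) ] - 1.960 )

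Here c is half the stated units, λ1 = 0.85 λ0, and y = unit size × share in age range × 1.9. The 1.9 is two years of follow-up with 10% lost per year (1 + 0.9).

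| Country | c | λ0 | y | k | Computed | Stated |
|---|---|---|---|---|---|---|
| Niger | 311 | 0.025 | 688 × 0.167 × 1.9 = 218.3 | 0.51 | 84.5% | 84% |
| Malawi | 153 | 0.005 | 1464 × 0.19 × 1.9 = 528.5 | 0.51 | 40.7% | 41% |

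Tanzania's 2016 unit size is blank in the text, so its 31% cannot be checked. With k = 0.4 and a 17% share, 31% implies about 316 people per unit (an assumption, used only in step 4).

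**2. Combine the stated powers.** Each power at 15% implies a non-centrality of z(power) + 1.960:

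- Niger: 0.994 + 1.960 = 2.954
- Malawi: -0.228 + 1.960 = 1.732
- Tanzania: -0.496 + 1.960 = 1.464

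With a country term and a common rate ratio, the squares add: 8.729 + 3.001 + 2.144 = 13.873, whose root is 3.725.

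**3. Rescale to 14% on the log rate-ratio scale.** ln(0.86)/ln(0.85) = 0.928.

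- Power at 14% = Phi(3.725 × 0.928 - 1.960) = Phi(1.497) = **93.3%**.
- Effect at 80% power = 1 - exp(ln(0.85) × 2.802/3.725) = **11.5%**.

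| Countries used | Power at 14% | Effect at 80% power |
|---|---|---|
| All three | 93.3% | 11.5% |
| Niger and Malawi | 88.8% | 12.4% |
| Niger alone | 78.3% | 14.3% |

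Moving all three stated powers by 2 points either way gives 91.9% to 94.5% at 14%, and 80% power at 11.8% to 11.2%.

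**4. Cross-checks.**

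- The SAP formula summed over countries gives 93.5% at 14% and 80% at 11.4%.
- The randomization lists imply 646 - 30 = 616 mortality units in Niger and 644 - 30 = 614 in Tanzania. With those counts the formula gives 93.3% and 11.4%.
- A simulated country-adjusted negative binomial likelihood-ratio test, with asymptotic cut-off and 600 runs per setting on 616, 306 and 614 units, gave 92.7% at 14% (SE 1.1), 83.2% at 11.5% (SE 1.5) and 5.0% under the null. A second simulation with 1,000 runs, the stated unit counts and 330 people per Tanzania unit gave 94.4% and 80.6%.

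**5. The planning statement does fit.** Three countries at 80% for 15% give sqrt(3) × 2.802 = 4.853. That yields 88.2% power at 10%, and 80% at 9.0%. Like for like, the detectable effect moved from about 9% to about 11.5%.

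**6. Where 80% at 14% might come from.** Niger alone comes close. So does a pool with no country term, in which rate differences between countries count as noise: the single formula with an overall CV of 0.94 gives 76% at 14% and 80% at 14.6%. Other weightings give 68% to 76%, and simulation without the country term gives 83%. With the planning rates, which are similar across countries, this unadjusted route gives 88.1% at 10%, the same as the adjusted one. The two routes part only once the country rates diverge, so step 5 does not show which was used.

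**7. The rate descriptions.** 0.005/0.0148 = 34% and 0.006/0.016 = 38%. Both rates are far below plan.

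**The case against.** The strongest reply is that the 2016 line does not claim to combine the three country powers. It gives no inputs, and the SAP states no common-effect assumption and plans a country-by-treatment analysis. Other inputs can land near 80%: one year of person-time gives 82%, and a pool without the country term gives 83% by simulation. The revision history also records a planned interim efficacy analysis, which could reduce the final alpha.

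These routes do not rescue the figure:

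- One year of person-time would not reproduce the stated country powers.
- Omitting the country term contradicts section 2.1.1.
- An interim would need a final alpha near 0.009 to bring 93% down to 80%. Alpha 0.025 still gives 88.8%, and the SAP states 0.05.
- Unequal effects do not help. With 14% in Niger, pooled power falls to 80% only if Malawi and Tanzania have about 7%, and the information-weighted overall effect is then 11.5%, not 14%.

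Several points do stand. The source of the figure is unknown. Any replacement should state the common effect and final alpha as conditions. The Tanzania formula check is circular, although step 2 does not need it, and dropping Tanzania narrows the gap in detectable effect from 2.5 to 1.6 points. The unit counts hardly affect power. The contingency SAP's observed Niger CV of 0.34 would widen the gap (97.7% at 14%, 80% at 10.1%), but it is later information and cannot fault a 2016 projection.

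**Conclusion.** The concern holds. The country figures can be checked for Niger and Malawi and are sound, so the pooled line is the one that does not fit. Under the planned country-adjusted model, pooled power at 14% is about 93%, not 80%, and 80% power is reached at about 11.5%, not 14%. This rests on a common relative effect, final two-sided alpha 0.05, and the June 2016 country powers as stated. Without Tanzania the conclusion is the same, at 88.8% and 12.4%.

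The error is conservative: the trial is better powered than its plan says, and no test, alpha or cluster count changes. It is still the only current statement of what the primary analysis can detect, and it exaggerates the loss since planning. It should be corrected, but nothing in the conduct of the trial depends on it.

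**What to change.** Replace the 2016 update in SAP section 3.1.3 with a statement of this kind: about 80% power for an overall effect of about 11.5% (about 93% for 14%), assuming a common relative effect, final two-sided alpha 0.05, and the June 2016 country rates, CVs and cluster counts, combined under the country-adjusted model. State the pooling method. If the 14% figure rests on other inputs, give them and explain how they agree with the country powers.

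In sections 3.1.1 and 3.1.3, describe the 2016 Malawi and Tanzania rates as lower than planned (0.005 against 0.0148; 0.006 against 0.016). Reconcile 622 with 616 units in Niger and 631 with 614 in Tanzania, noting that the effect on power is negligible.

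The cost is SAP wording only.
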